Participants: We aim to recruit 30 participants aged 65 years or above through convenience sampling at a senior activity centre in the Municipality of Aalborg. Inclusion criteria is age about 65, the ability to stand for 30 seconds without any aid and the ability to walk 8 meters. Exclusion criteria is dementia as this might affect the cognitive results. Activity centres tend to allure seniors with good physique, hence, there is a risk of selection bias using this type of sampling. We will try to minimize this risk by recruiting widely from the activity center and not only from the physical teams, i.e. gymnastics [12].

Setting and data collection: Testing will be performed at the activity centre on the NWBB [21] and the gait test on 8m [5] of hard floor without carpets or obstacles. Data will be registered in REDCap [22].

[figure not shown]

Figure 1. Drawing of WBB and gait test settings.

Procedure: The participant will attend two test days separated by 14 days. At the initial test day, participants will complete the Orientation Memory Concentration (OMC) test [23] and fill out a questionnaire to inquire baseline characteristics. The questionnaire include the Tilburg Frailty Scale (TFI) [24], Vulnerable Elders Survey 13 (VES- 13)[25], the Short Falls Efficacy Scale International [26] and questions regarding musculoskeletal complications, neurodegenerative diseases or complications, and use of medicines [3] [6] [7] [11]. Afterwards, participants will undergo the testing procedure includingsingle-task cognitive tests, single-task and dual-task gait , and single- and dual-task NWBB tests in a counter-balanced order

The cognitive tests include a supermarket test [27], an arithmetic test [2], and an animal test [2]. Each participant will complete three trials of 30 seconds of each test for a total of nine trials. The single-task gait test includes three trials of eight-meter walking, with the middle six meter being timed. During the single-task NWBB test, participants will be instructed to stand as still as possible for 30 seconds on a WBB for three trials. For the dual-task tests, the participants will perform the gait and NWBB conditions while carring out the before-mentioned cognitive tests simultaneously. Thus, the participants will conduct nine dual-task gait and NWBB tests, respectively. An overview of the testing procedure is provided in Figure 2.

At the second test day, the participants will perform the testing procedure again including the single-task cognitive test, the single- and dual-task gait test, and the single, and dual-task NWBB test. The order of the test will be identical to the order on the initial test day.

TESTS	COGNITION				
		Supermarket test	Arithmetic test	Animal test	No cognitive (single task)
	Cognitive test (single task)	1. Butcher products 2. Fruits & vegetables 3. Dairy products	1. 480 - 7 2. 420 - 7 3. 450 - 7	1. Birds 2. On land 3. Sea animals	
	Gait test (dual + single)	1. Dairy products 2. Butcher products 3. Fruits & vegetables	1. 220 - 7 2. 250 - 7 3. 280 - 7	1. On land 2. Sea animals 3. Birds	1. Time 1 2. Time 2 3. Time 3
	WBB test (dual + single)	1. Fruits & vegetables 2. Butcher products 3. Dairy products	1. 350 - 7 2. 320 - 7 3. 380 - 7	1. Sea animals 2. On land 3. Birds	1. Area + speed 1 2. Area + speed 2 3. Area + speed 3

Figure 2. Schematic overview of this study's tests.

Analysis: Data will be used for calculating the correlation between the gait test and the NWBB test using correct response rate (CRR) [8], dual task gait/balance cost (DTGC) and dual task cognition cost (DTCC) [7]. Agreement will be investigated through Bland-Altman plots [13] along with calculation of mean difference, paired t-test, and LOA. Correlation will be shown using Pearson's correlation. Analysis of intra-rater reliability will include interclass coefficient (ICC), coefficient variant (CV), limits of agreement (LOA), standard error of measurements (SEM) and mean difference including paired T-test.

Safety considerations: Participants will be followed closely through the gait test and the NWBB test. If participants are unable to walk 12x8m or unable to keep their balance for 12x30sec the investigator will interrupt the testing and they will be excluded from the study for safety reasons. Smaller breaks and single fails are accepted.

Reproducibility: The study is easily reproducible. Participants represents a wider part of the background population between elders above 65yo. Testing only includes a WBB and 8m of firm flat floor without obstacles.

Ethics: Participants will participate voluntarily with oral and written consent. The local ethics committee will have consulted, and the study will be registered at the Danish Data Protection Agency.

Time schedule:

Testing will be conducted throughout November 2020, and the study result will be presented as an article in 2021.

Funding:

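### Test order is counter-balanced but absent from the stated between-test analyses, so an order effect would widen the gait–NWBB limits of agreement

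*Protocol*

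**What the plan says.** The Procedure paragraph puts single-task cognitive tests, gait tests and "single- and dual-task NWBB tests in a counter-balanced order". It does not say how many sequences are used, which units are counter-balanced, or how participants are assigned to a sequence. For the second test day it adds: "The order of the test will be identical to the order on the initial test day".

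The Analysis paragraph compares the two tests on correct response rate (CRR), dual-task gait/balance cost (DTGC) and dual-task cognition cost (DTCC). "Agreement will be investigated through Bland-Altman plots [13] along with calculation of mean difference, paired t-test, and LOA". "Correlation will be shown using Pearson's correlation". Reliability between the days is described by ICC, CV, LOA, SEM and a mean difference with paired t-test. No order, sequence or period term appears in any of these.

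The sample is a target without a derivation: "We aim to recruit 30 participants aged 65 years or above".

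**The concern.** Counter-balancing stops an order effect from biasing the mean gait–NWBB difference, but it does not remove the effect from the data. Half the participants have their difference shifted one way and half the other. An analysis that ignores order counts that spread as disagreement between the tests.

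An order effect is plausible from Figure 2. The same three supermarket categories and the same three animal categories occur in the cognitive, gait and NWBB blocks, and every arithmetic trial subtracts 7. A participant therefore meets each semantic category three times in one session. There are also 12 walks and 12 stands per day, so fatigue is possible.

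The Background asks whether the NWBB test can stand in for the dual-task gait test. The between-test LOA and correlation are what answer that, and they are the statistics that counter-balancing does not protect.

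**Working it through.** **Inputs.** From the protocol: n = 30, counter-balanced order, the same order on both days, and the listed statistics. The protocol gives no order effect, SD, expected correlation or expected ICC, so there is no figure of its own to reproduce. Assumptions: two orders (gait first, NWBB first) with 15 people each; scores with SD 1 within an order; the test done second differs from the test done first by g SD, with g = 0.25 or 0.5; true r = 0.60 (0.80 as a check); true ICC = 0.70.

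**Model.** Let p = g/2. The first test is shifted by −p and the second by +p. Pooled over the two orders, each test's variance rises by p², the covariance between tests falls by p², and the variance of the difference rises by 4p² = g².

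**Mean difference.** The shifts are +g and −g in equal halves and average to 0, so there is no bias.

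**Between-test LOA.** Widening factor = √[(2(1−r) + g²) / (2(1−r))].
- g = 0.25, r = 0.60: √(0.8625/0.80) = 1.04.
- g = 0.5, r = 0.60: √(1.05/0.80) = 1.15. The half-width goes from 1.96 × √0.80 = 1.75 SD to 1.96 × √1.05 = 2.01 SD.
- g = 0.5, r = 0.80: √(0.65/0.40) = 1.27.

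The CI of the mean difference reported with the paired t-test widens by the same factor. At g = 0.5 and r = 0.60 it has the width expected from 30 × 0.80/1.05 = 22.9, or about 23, participants.

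**Correlation of a directly compared score such as CRR.** Observed r = (r − p²)/(1 + p²).
- g = 0.25: (0.60 − 0.0156)/1.0156 = 0.58.
- g = 0.5: (0.60 − 0.0625)/1.0625 = 0.51. A true 0.80 gives 0.7375/1.0625 = 0.69.

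**DTCC.** Both costs subtract the same single-task cognitive score. Take all six orders of the three blocks, a shift of e SD per position, and cost as a simple difference. The order part then has variance 2e² in each cost and covariance e² between them, so observed r = (r + e²)/(1 + 2e²). At e = 0.4, a true 0.20 becomes 0.36/1.32 = 0.27 and a true 0.80 becomes 0.96/1.32 = 0.73. The correlation moves toward 0.5 from either side. The LOA still widen: √(1.92/1.60) = 1.10 and √(0.72/0.40) = 1.34.

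**Reliability.** With order effects d₁ and d₂ on the two days, observed ICC = (ICC + d₁d₂/4)/(1 + (d₁² + d₂²)/8).
- Full recurrence, d₁ = d₂ = 0.5: 0.7625/1.0625 = 0.72.
- Present on day 1 only, d₁ = 0.5 and d₂ = 0: 0.70/1.03125 = 0.68.
- The ICC rises only if d₂/d₁ exceeds (1 − √(1 − 0.70²))/0.70 = 0.41.
- Under full recurrence the error variance is 1.0625 × (1 − 0.7176) = 0.30, the same as 1 − 0.70. The retest SEM and LOA do not change.

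**Does adjustment work?** In a simulation of 5000 studies (n = 30, 15 per order, r = 0.60, g = 0.5), the mean raw results were r = 0.495 and LOA ±2.00 SD. After removing the order means they were 0.591 and ±1.74 SD. With no order effect they were 0.592 and ±1.74 SD.

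**The case against.** **The SAP is not shown and could add an order term.** That is possible, and the protocol does not say that order will be ignored. But the protocol does name its analyses, and as named they do not use a factor that its own design created. The point concerns those stated choices.

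**The day-2 sentence is not an error.** This stands. Repeating the order holds test conditions constant at retest.

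**A reader might infer that ignoring order makes reliability look better than it is.** The documents do not support that. The ICC rises only if much of the effect recurs on day 2. If it is mainly practice with categories first met on day 1, the ICC falls. Where the ICC does rise, the rise is about 0.02 at 0.5 SD, and the retest SEM and LOA, which are also planned, do not move.

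**A reader might also infer that every correlation is lowered.** That is not so either. DTCC can move both ways. An order effect with the same sign on both tests, for instance from doing single-task before dual-task trials, would raise r slightly at 0.5 SD, (0.60 + 0.0625)/1.0625 = 0.62, and leave the between-test LOA unchanged. For DTGC, a shift common to a test's single- and dual-task trials would largely cancel from the cost.

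**The sizes are assumed.** This also stands. Figure 2 contains some mitigation: arithmetic starting numbers differ in every block and the category order varies. The true effect may be small, which is why a range is shown.

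**Conclusion.** The point holds for the between-test analyses. The mean difference is unbiased, but the paired t-test, raw LOA and raw Pearson correlation leave order variance in the error. For a directly compared score, with two equal orders, an order effect of 0.25 to 0.5 SD on whichever test comes second and a true r of 0.60, the LOA are about 4% to 15% wider and r shows as 0.58 to 0.51. At 0.5 SD and r = 0.80 the LOA are 27% wider. This would count against the NWBB as an alternative for a reason that comes from the test session and not from the tests.

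For reliability there is no established fault. The effect on the ICC is small and its direction depends on whether the order effect persists to day 2.

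**What to change.** - Record each participant's test order as a data item, and state how many sequences are used and what is counter-balanced.
- Estimate the between-test mean difference with its 95% CI from a linear model of the gait–NWBB difference on a centred gait-first/NWBB-first indicator (+½ and −½). The intercept is then the mean difference averaged over the two orders.
- Take the between-test LOA from that model's residual SD.
- Report the correlation as a partial correlation given order, next to the unadjusted one.
- For reliability, keep the stated analysis. Add, as a sensitivity analysis only, an ICC from a mixed model with order, day and order-by-day as fixed effects and participant as random.

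The cost is a few lines of analysis text, no new data and about one degree of freedom with n = 30. Modelling all six possible block orders separately would cost five degrees of freedom with about 30/6 = 5 people per sequence, so the two-level indicator is the better choice for a sample of this size.
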